#### 4.7 Partial Dates

Missing or incomplete dates will not be imputed at the data level. However, assumptions for missing or partial dates for important variables will be made to allow inclusion of appropriate data records in the analyses. In general, the assumptions about the missing or partial dates, when needed, are made conservatively to avoid overestimation of treatment effects and underestimation of adverse effects.

If a medication, procedure or surgery date is missing or partial, so it cannot be determined whether it was taken prior or concomitantly, it will be considered both as a prior and a concomitant medication, procedure or surgery.

If the partial AE onset date information does not indicate whether the AE started prior to treatment or after treatment, the AE will be classified as started after treatment.

Confidential

## 4.8 Methods To Be Used For Handling Missing Data

When summarizing categorical variables, subjects with missing data are generally not included in the calculations of percentages unless otherwise specified. When needed, the category of "Missing" is created and the number of subjects with missing data is presented.

When summarizing continuous variables, subjects with missing data are not included in calculations. No imputations are made.

## 4.9 Changes to Analyses Specified in the Protocol

The tumor response categories criteria specified in Section 8.1 of this SAP are different than what is provided in the Sections 10.3.6 and 10.3.7 of the Protocol (Rev-15, 21 Feb. 2020). The tumor response categories and criteria provided in this SAP will be used.

## 5 Study Subjects

### 5.1 Disposition of Subjects

The number of subjects in each population will be tabulated by cohort (defined in Section 0), overall and subgroups (defined in Section 4.4).

The frequency of subjects treated, of subjects who completed the study treatment per protocol and of subjects who discontinued the study early will be given by cohort and overall for the ITT population. The primary reason for early discontinuation of study will be summarized. The details of the 'other reason' will be included in the listing.

### 5.2 Protocol Deviations

All protocol deviations will be assessed and identified by the sponsor. The major protocol deviations will be summarized for each cohort and overall for the ITT population. The details will be listed by subject and cohort. Listing of all in- and exclusion criteria not met will be provided by cohort separately.

## 6 Demographic and other Baseline Characteristics

Descriptive statistics with respect to demographics and subject characteristics at baseline will be displayed by cohort, overall, and subgroups (as needed, defined in Section 4.4) for the ITT population.

The variables to be summarized are:

- Age, gender, race, ethnicity
- Iris color, study eye,
- Tumor lesion thickness, tumor largest basal diameter, distance from the fovea, distance from the nerve, Risk factors
- History of Primary Choroidal Melanoma:
  - Eye affected (OS/OD/OU)
  - Time since diagnosis of CM (months)
  - Prior Treatment for CM (Yes/No)
- Vital signs: pulse, systolic and diastolic blood pressure (seated)
- Anti-drug antibody (ADA) sample
- Visual acuity score both in the study eye and in the fellow eye

Confidential

- Ophthalmic history (other than primary CM) both in the study eye and in the fellow eye
- Medical history (other than ophthalmic history)

Medical and ophthalmic history will be coded using the Medical Dictionary for Regulatory Activities (MedDRA) version 20.0 and will be tabulated by system organ class (SOC) and preferred term (PT) by cohort and overall for the ITT population. Multiple occurrences of the same preferred term in one subject will be counted only once. Summary tables will be sorted alphabetically by SOC then by PT within SOC based on descending frequency in the 'overall' column.

Other baseline data, for example, childbearing potential and contraception, serum pregnancy test, etc, will be provided in a data listing.

## 7 Prior and Concomitant Treatment

Prior and concomitant treatments will be summarised and listed for the ITT population.

### 7.1 Prior and Concomitant Medications

Prior and concomitant medications will be classified according to World Health Organization Drug Dictionary (Version 2017-March).

The number and percentage of subjects receiving a prior or concomitant medication will be displayed by first level Anatomical Therapeutic Chemical class (ATC 1) and fourth level Anatomical Therapeutic Chemical class (ATC 4) by cohort and overall for the safety population.

Medications will be reported as prior when they start before the first day of study treatment. Medications will be reported as concomitant when they start before, on or after first day of study treatment and continue afterwards. Medications started before the first day of study treatment and continuing afterwards will be reported both as prior and concomitant. In case of missing or partial start/stop date, rules defined in section 4.7 will be applied to identify prior and/or concomitant medications.

Prior and concomitant medication summaries will be sorted alphabetically by ATC 4 class within ATC 1 class.

A listing of all medications recorded on the prior and concomitant medications eCRF page will provide details including indication, start and stop dates and when available, dose, route, frequency.

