8.3.1. Concomitant Steroid Treatment

On study Day 1, ie, day of first administration of AU-011 treatment and before the first laser administration, the Investigator should begin topical 1% prednisone acetate or difluprednate 0.05% topical eye drops and an oral prednisone taper or periocular steroid injection. Subtenon's injection of triamcinolone acetonide (40mg/ml) can be given with up to 1 ml delivered as tolerated. Oral prednisone starting at 60 mg/day and tapering off (for example, over six to eight weeks) can also be used.

These regimens are intended to be a minimum treatment regimen and the Investigator can treat with higher doses than proposed in the guidelines in order to minimize the severity and duration of posterior segment inflammation and allow Cycle 2 of AU-011 therapy to be administered at 12 weeks or as soon as possible thereafter.

If posterior synechiae develop, the Investigator can also start mydriatric agents like mydriacyl, cyclogyl or atropine and miotic inhibitors like phenylephrine.

In the event of any potential breakthrough inflammation, the Investigator may restart clinically appropriate levels of oral prednisone treatment. Additionally, the Investigator may choose to taper subjects more quickly than described above.

If a subject continues to show inflammation during the active treatment period, the Investigator should determine the necessity of increasing the oral prednisone dose to 80 mg daily with slow taper or hospital admission with 250 mg intravenous methylprednisolone 4 times per day over 3 days to protect the eye and vision.

When Cycle 2 or additional therapy of AU-011 is administered, topical prednisone acetate 1% or difluprednate 0.05% topical eye drop taper and periocular steroid injection or oral steroid use should be instituted on the day of the first AU-011 treatment and before the first laser application. The topical steroid eye drop can be tapered and discontinued at the discretion of the Investigator. The periocular or oral steroid may consist of a periocular triamcinolone acetonide (40mg/ml) injection up to 1 ml as tolerated or an oral steroid taper similar to the oral taper described for Cycle 1 of therapy above. These regimens are intended to be a minimum treatment regimen and the Investigator can treat with higher doses than proposed in the guidelines, but not with lower doses.

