#### 4.6 Calculated Variables

- Study day 1 is defined as the day when first study treatment was received.
- The baseline is defined as the last assessment done before or on study day 1. For instance, if data was collected at screening and Day 1, then the Day 1 value will be used for baseline
- Time since diagnosis of CM (months) = (month and year of screening – month and year of diagnosis).

Assessments done on the date of study treatment administration are assumed to take place before the administration, unless specified otherwise.

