### 7.2 Prior and Concomitant Procedures/Surgeries

Prior and concomitant procedures and surgeries will be coded using MedDRA version 20.0.

The number and percentage of subjects undergoing a prior or concomitant procedure or surgery will be displayed by system organ class and preferred term by cohort and overall for the safety population.

Procedures and surgeries will be reported as prior when they start before the first day of study treatment. Procedures and surgeries will be reported as concomitant when they start before, on or after first day of study treatment and continue afterwards. Procedures and surgeries started before the first day of study treatment and continuing afterwards will be reported both as prior and concomitant. In case of missing or partial date, rules defined in section 4.7 will be applied to identify prior and/or concomitant procedures and surgeries.

Prior and concomitant procedures and surgeries summaries will be sorted alphabetically by SOC then by PT within SOC based on descending frequency in the 'overall' column.

Confidential

A listing of all procedures and surgeries recorded on the prior and concomitant procedures and surgeries eCRF page will provide details including indication, eye, and start and stop dates.

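### SAP 7.1 and 7.2 leave an item given only on Day 1 neither prior nor concomitant, so a Day 1 periocular steroid injection is missing from the summary tables

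*SAP*

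**What the plan says.** SAP Section 4.6 fixes the reference day: "Study day 1 is defined as the day when first study treatment was received". Section 7.1 then gives two rules. For prior: "Medications will be reported as prior when they start before the first day of study treatment". For concomitant: "Medications will be reported as concomitant when they start before, on or after first day of study treatment and continue afterwards". Section 7.2 uses the same construction: "Procedures and surgeries will be reported as concomitant when they start before, on or after first day of study treatment and continue afterwards".

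Section 4.7 has a fallback for dates that are missing or too incomplete to decide the class. In that case the item is counted in both: "it will be considered both as a prior and a concomitant medication, procedure or surgery". It says nothing about complete dates.

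Protocol Section 8.3.1 sets the steroid cover for the first day of AU-011, before the first laser application: "the Investigator should begin topical 1% prednisone acetate or difluprednate 0.05% topical eye drops and an oral prednisone taper or periocular steroid injection". Of the injection it says: "Subtenon's injection of triamcinolone acetonide (40mg/ml) can be given with up to 1 ml delivered as tolerated". For Cycle 2 or additional therapy, drops are again paired with either a periocular injection or an oral course, timed as follows: "oral steroid use should be instituted on the day of the first AU-011 treatment and before the first laser application".

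**The concern.** The two SAP rules should between them place every item that could have been in use from the first treatment day onward. They do not. An item given once, on Day 1, does not start before that day and does not continue past it. If its dates are complete, no rule picks it up. An item with unusable dates, by contrast, is counted twice.

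The gap matters because the protocol itself can produce such an item. Steroid cover is part of the background against which ocular inflammation is read, and safety of one or two treatment cycles is the primary objective. Drops go with both steroid options, so the drops row cannot show which option was used. A subject given drops and a Day 1 injection, as the protocol allows, would appear in the tables with drops alone. The same injection given at a later course would be tabulated. A difference between cohorts in recorded steroid use could then come from the counting rule alone.

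**Working it through.** The plan gives no figure to reproduce. The check is one of logic.

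**Rules in symbols.** Let s be the start day and e the stop day, with the first treatment day numbered 1. Read literally, prior means s < 1, and concomitant means any s with e > 1. This takes the continuation in Sections 7.1 and 7.2 to mean continuation past the first treatment day.

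**Where the rules leave a gap.** I took 12 days from screening to Week 104: -28, -7, -1, 1, 2, 8, 9, 15, 16, 29, 85 and 728. Pairs with the stop on or after the start number 12 × 13 / 2 = 78. Exactly one pair is neither prior nor concomitant: s = e = 1.

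**Steroid components of Protocol 8.3.1.** The stop day for the drops (Day 29) is my assumption. The oral taper uses the protocol's example of six to eight weeks: 1 + 42 = 43 and 1 + 56 = 57. Day 85 is the SAP target day for Week 12, the earliest visit for Cycle 2.

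| Item | s | e | Prior (s < 1) | Concomitant (e > 1) |
|---|---|---|---|---|
| Topical drops | 1 | 29 | no | yes |
| Oral taper, 6 weeks | 1 | 43 | no | yes |
| Oral taper, 8 weeks | 1 | 57 | no | yes |
| Periocular injection, Day 1 | 1 | 1 | **no** | **no** |
| Periocular injection, Cycle 2 | 85 | 85 | no | yes |

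**By subject.** Suppose the injection is chosen at the start of each course.

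| Subjects | Injection days | Counted as having had an injection? |
|---|---|---|
| Cohorts 1, 2, 3, 6 (single dose) | 1 | no |
| Cohorts 4, 5, 7, 8, 9 (repeat dose, one cycle) | 1 | no |
| Cohorts 10, 11, 12 (two cycles) | 1 and 85 or later | yes, through Cycle 2 |

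A subject in Cohorts 1-9 who later has additional AU-011 with an injection moves to the last row. A subject in Cohorts 10-12 who never reaches Cycle 2 behaves like the first two rows.

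**With the proposed rule (e ≥ 1, or ongoing).** None of the 78 pairs is unclassified. The Day 1-only record becomes concomitant. The three pairs that start on Day -28, -7 or -1 and stop on Day 1 change from prior only to both. No other pair changes.

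**The case against.** The best answer is that the authors did not mean to exclude Day 1 items. Section 7.1 lists the first treatment day among the permitted start days for a concomitant medication. The sentence that follows applies continuation to items begun earlier, which is where the condition does useful work. On that reading there is no gap. It is a fair guess at intent, but the condition as written governs all three start times, and a programmer who follows it will drop the record.

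The second answer is that little is lost, and most of this stands. The injection is an alternative to an oral taper, not a requirement. Drops and oral courses remain in the tables. The listings cover every recorded medication and procedure with its dates. A missing or partial stop date may bring in the Section 4.7 fallback. No endpoint uses the prior/concomitant class; SAP Section 8.1.4 takes standard-of-care dates directly from the procedure page. The medication table is by drug class, so how visible the omission is also depends on how the injection is coded, which the documents do not say.

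A reader might infer more than the documents support:

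- **That single-dose cohorts are hit hardest.** This would be true of a one-day item repeated on every dosing day, since the Day 8 and Day 15 records would be counted. Protocol 8.3.1 starts steroid cover once per course, with no distinction between single and repeat dosing, so Cohorts 4, 5 and 7-9 lose the Day 1 injection just as Cohorts 1, 2, 3 and 6 do.
- **That one-day treatments to lower intraocular pressure vanish in the same way.** The protocol sets a pressure ceiling, only for the 80 µg cohorts (Section 10.3.2), and the passages that state it describe no such treatment.
- **That the tables would show 0% in some cohorts and 100% in others.** That needs a one-day item given to every subject at every treatment visit. The documents describe none.

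**Conclusion.** The gap holds on the literal text, for medications and procedures alike, and it reaches one item that the protocol names. Its effect is an incomplete descriptive table, with a possible artificial contrast between subjects given one course of AU-011 and subjects given more than one. It does not separate single-dose from repeat-dose regimens.

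The conclusion assumes that the SAP sentence is programmed as written and that the injection is entered with the same complete start and stop date. The contrast between courses also assumes that the injection was chosen for at least some later courses. The number of subjects who received it cannot be worked out from the documents. This is a minor correction and casts no doubt on any efficacy or safety endpoint.

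**What to change.** In SAP Sections 7.1 and 7.2, define concomitant as any medication or procedure that is ongoing, or whose stop date falls on or after the first day of study treatment, and state that this includes items given only on Day 1. Leave the definition of prior unchanged. Items begun earlier and stopped on Day 1 will then appear in both tables, which is appropriate.

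The cost is one sentence in each of two sections and one changed comparison in the program. No new data are needed.

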### 7.2 Prior and Concomitant Procedures/Surgeries

Prior and concomitant procedures and surgeries will be coded using MedDRA version 20.0.

The number and percentage of subjects undergoing a prior or concomitant procedure or surgery will be displayed by system organ class and preferred term by cohort and overall for the safety population.

Procedures and surgeries will be reported as prior when they start before the first day of study treatment. Procedures and surgeries will be reported as concomitant when they start before, on or after first day of study treatment and continue afterwards. Procedures and surgeries started before the first day of study treatment and continuing afterwards will be reported both as prior and concomitant. In case of missing or partial date, rules defined in section 4.7 will be applied to identify prior and/or concomitant procedures and surgeries.

Prior and concomitant procedures and surgeries summaries will be sorted alphabetically by SOC then by PT within SOC based on descending frequency in the 'overall' column.

Confidential

A listing of all procedures and surgeries recorded on the prior and concomitant procedures and surgeries eCRF page will provide details including indication, eye, and start and stop dates.

## 8 Efficacy Evaluation

Efficacy will be assessed at each visit for any potential tumor response based on imaging-based assessments, and changes in Early Treatment Diabetic Retinopathy Study (ETDRS) BCVA. No formal hypothesis testing will be performed in this study.

For imaging-based measurements, e.g. B-scan, OCTA, etc, as there are 2-3 readers and multiple values are available, and no adjudication will be conducted, a general convention will be followed: For the continuous variables, the average will be taken as the final value for analysis. For the categorical variables, if there are two like responses available, it will be the final response. And when all responses differ, the most conservative response will be taken as the final response.

Efficacy analyses will be performed by cohort, overall and for subgroups (defined in Section 4.4) on ITT population. Some efficacy analyses will also be performed on Efficacy Evaluable population as sensitivity analyses (see more details in Section 8.3).

### 8.1 Tumor Response

Three different methods of determining tumor response will be applied. The rationale for using these 3 methods is to describe the data taking into consideration various factors (ie, criteria as stated below) that could have impacted the determination of tumor response. The following four criteria will be considered for tumor response assessment:

- a) The maximum thickness and LBD as defined in Section 8.1.1
- b) The investigator determination of the subject meeting protocol defined disease progression criteria as defined in Section 8.1.2
- c) The subject having an AE of Pigmentary Changes as defined in Section 8.1.3.
- d) The subject receiving standard of care

The 3 different methods for determining tumor response are:

#### 1. Based on maximum thickness and LBD and subject receiving Standard of Care

Tumor response (PR, SD, or DP) will be based on the algorithm as defined in Section 8.1.1, with the modification that Investigator determination mentioned in DP definition will not be considered and if a subject receives standard of care they will be considered as having met the disease progression (DP) criteria from the date standard of care was administered.

Note that for the Month 12 LOCF and Last Visit timepoints:

- If a patient receives standard of care prior to their Month 12 Visit, the subject will be considered as having met DP, even if the LBD and/or tumor thickness assessments are being LOCF'd from a time-point previous to the SOC being administered.
- Similarly, if a patient receives standard of care prior to their Last Visit, the subject will be considered as having met DP, even if the LBD and/or tumor thickness assessments are being LOCF'd from a time-point previous to the SOC being administered.

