8.3.3. Additional Therapy

Additional therapy with AU-011 at the maximum tolerated and feasible dose of 3 repeat doses of 80 µg each followed by two laser applications (treatment regimen) can be provided to:

- ensure that all subjects are able to receive the maximum tolerated and feasible dose, particularly for subjects that were treated with lower doses previously
- allow additional treatment regimens in subjects that have stable disease (treatment extension)
- allow retreatment in subjects that meet the protocol definition of disease progression

If the fovea is near the tumor edge, an adjustment to the laser procedure should be performed on each treatment day as outlined in section 8.2.2 and the Injection and Laser Procedure Manual. Subjects may be considered for additional therapy with AU-011 (defined above) after Visit 11 (Week 12) and only after inflammation from the previous treatment has resolved or when the inflammation is minimal and decreasing based on investigator judgement. Additional therapy with AU-011 must be approved by the Sponsor on a case-by-case basis prior to the initiation of therapy. Alternatively, also after Visit 11 (Week 12 Visit), standard of care therapy, including plaque brachytherapy, proton beam radiotherapy or enucleation may be used if the subject meets the protocol definition of disease progression or the Investigator judges that the disease is progressing per their clinical judgement for increases in tumor thickness or LBD that are less than the protocol definition of disease progression. Before additional therapy is performed, the following protocol assessments must be collected in the study eye unless otherwise noted: ETDRS BCVA (both eyes), slit lamp biomicroscopy, IOP measurement, fundoscopy, Fundus photos, EDI-OCT, B-scan ultrasound, A-scan ultrasound, OCTA (Cohorts 6 to 9 only) and a visual field examination. If these assessments have not been performed at the most recent study visit, an unscheduled visit is required to be performed to obtain these assessments.

The criteria for implementing additional therapy due to disease progression is as follows:

• An increase on B-scan ultrasound of >0.5 mm in melanoma thickness from baseline, not due to intralesional hemorrhage/inflammation

OR

• An increase on digital fundus photos of >1.0 mm in melanoma diameter from baseline, not due to intralesional hemorrhage/inflammation or pigmentary changes

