#### 8.1.4 Subjects Receiving Standard of Care

The date of the subject receiving standard of care will be from the Prior and Concomitant Procedure/Surgery eCRF page. Standard of Care includes the eye procedures categorized as: 'Radiotherapy to eye', 'Brachytherapy to eye' or 'Photodynamic therapy' (i.e., dictionary derived terms).

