### 8.3 Sensitivity Analyses

The following sensitivity analyses will be performed:

- The maximum tumor thickness and largest basal diameter endpoints (i.e., as described in Sections 8.1.5 and 8.1.6, respectively) will be summarized on ITT population excluding post-standard of care data (i.e. all data after receiving standard of care will be excluded for the standard of care subjects).
- BCVA data (Section 8.2) will be summarized on ITT population excluding post-standard of care data. Number and percentage of subjects with a 5, 10 or 15 letter gain or loss at each visit up to the Week 52 visit and at the end of study visit will also be provided for: 1) Efficacy Evaluable population; 2) Efficacy Evaluable population excluding post-standard of care data.
- Tumor response (section 8.1.7) will be summarized on Efficacy Evaluable population.

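### Tumor response scores standard of care as progression but has no rule for non-planned AU-011 given after progression, so a retreated progressor can count as tumor control in the original cohort

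*SAP*

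**What the plan says.** **Response rules.** SAP 8.1 states that "The following four criteria will be considered for tumor response assessment": thickness and largest basal diameter (LBD), the Investigator's determination of progression, an adverse event of pigmentary change, and receipt of standard of care. Under Method 1, "if a subject receives standard of care they will be considered as having met the disease progression (DP) criteria", counted from the date it was given. Methods 2 and 3 build on Method 1, and Method 3 is the primary method for the study report. SAP 8.1.4 limits standard of care to radiotherapy, brachytherapy or photodynamic therapy to the eye. AU-011 is not named there, and SAP 8.1.2 and 9.6.7 treat it as separate from standard of care.

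**Later AU-011.** Protocol 8.3.3 permits "Additional therapy with AU-011 at the maximum tolerated and feasible dose of 3 repeat doses of 80 µg each followed by two laser applications" after Week 12, once inflammation has resolved or is minimal and decreasing, and with Sponsor approval case by case. It gives three purposes: to "ensure that all subjects are able to receive the maximum tolerated and feasible dose, particularly for subjects that were treated with lower doses previously", to extend treatment in stable disease, and to "allow retreatment in subjects that meet the protocol definition of disease progression".

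**Reporting.** Baseline is fixed at first treatment (SAP 4.6). Efficacy is shown by cohort, overall and by subgroup (SAP 8). Response is shown at each visit and, in an overall summary, at Month 12 LOCF and Last Visit.

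**Sensitivity analyses.** For thickness and LBD, SAP 8.3 specifies that "all data after receiving standard of care will be excluded for the standard of care subjects", and BCVA has a similar exclusion. For tumor response the only sensitivity analysis changes the population, by leaving out site 009.

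**The concern.** Progression under the assigned regimen can lead either to standard of care or to another AU-011 course. SAP 9.6.7 describes both as following an Investigator's finding of progression, yet only standard of care is scored as failure. A good result after retreatment can then be read as tumor control by the first regimen.

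The first secondary objective is efficacy with one or two cycles at the maximum safe and feasible dose. In Cohorts 1 to 7 additional AU-011 is a different regimen from the one assigned. In Cohorts 8 and 9 it is an unplanned second cycle of the same regimen, which blurs one cycle against two. The subgroup of Phase 3 eligible subjects with two cycles (SAP 4.4) is defined by having received two cycles, and does not say whether a second course given for progression qualifies.

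**Working it through.** The plan gives no sample size formula, power or retreatment count to reproduce. The check applies the written classification rules to an example and then works out the effect of one subject on a control rate.

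**Step 1. Classification.** Inputs from SAP 8.1.1: progression (DP) is an increase above 0.5 mm in thickness or above 1.0 mm in LBD; partial response (PR) is a reduction above 0.5 mm in either, with no progression in the other; stable disease (SD) is the range between. Example: thickness is +0.7 mm at Week 26, LBD is unchanged throughout, and later treatment is given before Month 12.

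| Later treatment | Thickness change at Month 12 | Method 1 | Methods 2 and 3 |
|---|---|---|---|
| Standard of care | any | DP | DP |
| AU-011 | +0.4 mm | SD | SD |
| AU-011 | -0.6 mm | PR | PR |
| AU-011 | +0.7 mm | DP | SD if the eCRF answer is No, otherwise DP |

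**Step 2. Why nothing restores the earlier DP.** Baseline is not reset. The LOCF rule in SAP 8.1.1 fills only missing thickness or LBD values, and no text carries an earlier DP forward to Month 12 LOCF or Last Visit.

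**Step 3. Why the last row can turn to SD.** The eCRF question in SAP 8.1.2 is compound. It asks whether the subject met the progression criteria and has not yet had standard of care or additional AU-011 since the previous visit. Once AU-011 has been given, No is a literal answer even if the tumor is above the limits, and No converts measured DP to SD. The override in the same section covers standard of care only. A missing judgement takes the next non-missing one, so a No recorded after retreatment could also be applied back to the progression visit.

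**Step 4. Planned exclusions.** SAP 8.3 and the table list in SAP 11.3.1 contain versions of thickness, LBD and BCVA without data after standard of care. None removes data after additional AU-011. The visual acuity failure rule in SAP 8.2 also censors at standard of care only.

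**Step 5. Size.** If k subjects in a group of n move from DP to control, the shift in percentage points is 100 × k / n.

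| Group | n | k = 1 | k = 3 |
|---|---|---|---|
| One escalation cohort | 3 | 100 × 1/3 = 33.3 | 100.0 |
| Expanded escalation cohort | 6 | 100 × 1/6 = 16.7 | 50.0 |
| Cohort 9 (up to 12) | 12 | 100 × 1/12 = 8.3 | 25.0 |
| Cohorts 1 to 8 (8 × 3) | 24 | 100 × 1/24 = 4.2 | 12.5 |
| All subjects (about 60) | 60 | 100 × 1/60 = 1.7 | 5.0 |

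The values of k are assumptions. The k = 3 column needs three subjects in the group to progress, be approved for AU-011 rather than sent to standard of care, and then read as control.

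**The case against.** The other side has a good case on weight. The primary objective is safety, there is no hypothesis test or success threshold, and protocol 10.5 reports status at each visit rather than progression-free status. On that view, SD at Week 52 is a true statement about Week 52. A subject above the limits at Week 26 is still DP in the Week 26 Method 1 table. Additional AU-011 is counted by original cohort (SAP 9.6.7) and listed by subject, as are the imaging values, so a careful reader of a 3-subject cohort could find the cases.

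All of this stands, and it limits the harm. It does not explain why standard of care overrides the measurement at Month 12 LOCF and Last Visit while AU-011 after progression does not. Nor do a safety count and listings show the effect on the control rate.

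A reader might go further and infer that the results of Cohorts 1 to 7 are really those of the later regimen. The documents do not support this: approval is case by case, inflammation must have settled or be minimal and decreasing, and no retreatment is reported. Nor are these cohorts the main evidence for efficacy at the maximum dose.

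A reader might also infer that all later AU-011 is treatment failure. Protocol 8.3.3 allows it in stable disease and to reach the maximum dose, and Cycle 2 in Cohorts 10 to 12 is planned treatment.

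**Conclusion.** The point holds as an asymmetry in the response rule, and it should be fixed. Under all three methods, a subject who progresses, receives non-planned AU-011 and is back within limits counts as tumor control for the original cohort at Month 12 LOCF and Last Visit. In Methods 2 and 3, including the primary method, this can also happen with the tumor still above the limits. No planned efficacy table shows the effect.

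Each such subject adds 1/n to the control rate: 33 points at n = 3, 8 at n = 12, 1.7 at n = 60. Whether there are any such subjects is not stated. Compared with scoring them as DP, the present rule can only leave the control rate unchanged or raise it. For BCVA the direction is unknown.

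It would be too strong to say that the reported rates are biased by a known amount, or that an error rate is affected. The study is descriptive, and what is at stake is how tumor control is attributed to a regimen.

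**What to change.** Add the following to the SAP, labelled as introduced after the first database lock (SAP v5.0 already postdates that lock).

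1. In SAP 8.3, add thickness, LBD, BCVA and tumor response tables that exclude data after any non-planned AU-011 or standard of care, whichever comes first.
2. Add a version of the overall response summary with a further rule. A subject who met the SAP 8.1.1 thickness or LBD progression limits, on measurements up to and including the pre-retreatment assessment, and then received non-planned AU-011 is DP from the retreatment date, with a separate category.
3. In that version, extend the standard-of-care override in SAP 8.1.2 to these subjects, so that a No answer cannot return them to SD.
4. State that planned Cycle 2 in Cohorts 10 to 12, and AU-011 given without prior progression, are not DP.

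The rule uses measurements because the documents do not show an eCRF field for the reason for retreatment; protocol 8.3.3 requires progression and subsequent treatment to be recorded. The same section requires B-scan and fundus photographs before additional therapy, so the inputs should exist. One consequence is that a subject above the limits because of swelling or pigment change, then given AU-011 for another reason, would be DP in this version. The separate category keeps such cases visible.

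The cost is SAP wording, a few extra tables and a possibly less favourable control rate, which may be material in 3-subject cohorts.
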